**Figure 3. Study Flow Chart**

**Figure 2. Flow of Program Contents up to 6 weeks**

[figure not shown]

Safety of the program will be monitored by tracking self-report of falls, injuries, and adverse events. Participants will record falls or other adverse events in their tracking system, or Action Plan. They will be instructed to report all events to the clinical investigators. In addition, the research assistant will conduct calls bi-weekly telephone calls to collect these data.

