### **Adverse Event Recording from the Baseline Data Collection through Week 6 (in-person classes)**

Because this study includes older adults at increased risk for falls, we expect adverse events in this study to include falls. In addition, we expect adverse events from exercise in both groups to include: fatigue, muscle soreness or other discomfort or a fall or injury during tests and exercise. As per Lamb 2005, falls will be described as "unexpected events in which the participants come to rest on the ground, floor, or lower level." Participants will be provided with the definition of falls used in this study in the Baseline Data Collection & Orientation session (prior to starting the program). They will be provided with their binders, and we will instruct them in the use of the Action plan to record daily any falls or adverse events, symptoms and questions, as they occur. At each session, the instructor will collect the forms, make copies for study documentation, and return them to the participants.

If participants report fall(s) and/or adverse effects/events through the Action Plan (intervention) or Activity Tracker (control), or verbally, in-person or by telephone, the instructor will provide appropriate clinical assessment and recommendations and modifications if safe to continue participating in the program and document in the clinical flow chart. In addition, the instructor will fill out the Adverse Event Form (Appendix P) and provide the form to the research assistant, who will document the event in a master log of all adverse events.

If a participant falls or experiences an adverse event while attending the class session, the instructor will provide appropriate clinical assessment and recommendations and modifications if safe to continue participating in the program and document in the clinical flow chart. If injury occurred and the participant was unable to participate in the class, the instructor will complete and submit an RL Solutions event as per Mt Ascutney procedures. The instructor will determine

whether the participant needs to seek medical attention at MAHHC and assist the participant to the clinic or emergency department. In addition, the instructor will fill out the Adverse Event Form (appendix P) and provide the form to the research assistant for documentation in the master log.

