### **Adverse Event Recording from Week 6 through Study Completion (6 months)**

To identify adverse events after the regular class sessions have been completed, participants will record the events in their tracking forms, and a blinded assessor (separate from the outcomes assessor, study management and intervention teams) will contact the participants every 2 weeks by telephone to inquire about any events that have occurred. A standard script will be followed during these sessions to obtain consistent information and to maintain blinding (appendix P). The blinded assessor will fill out the Adverse Event Form for any event reported during a call and provide it to the research assistant for documentation and tracking. If the adverse event meets the definition of Unanticipated Problem, the blinded assessor will also notify the principal investigator immediately (same day). The principal investigator will report the Unanticipated Problem according to the BU IRB guidelines stated above. In addition, other study staff will report adverse events if they become aware of them during the post-group class time period (Week 6 – 6 Months) by filling out the Adverse Event Form, providing it to the research assistant, and notifying the principal investigator immediately if the event is an Unanticipated Problem.

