### 6 Week Data Collection Assessment (See Appendix S)

Both Groups		Intervention Only	Control Group Only
Performance-based	Self-Report		
4-stage Balance	LLFDI community mobility short form or CAT		
TUG	FES-I		
30-second Chair Stand	ABC-6		
DGI	Barriers Self-Efficacy		
	Get up from floor		
	Exercise Adherence: walking, strength, balance (from Action Plan/Tracking doc)	6-wk Intervention program evaluation questions	6 week Healthy YOUiversity program evaluation questions
	Falls (from Action Plan/Tracking doc)		
	Adverse Events (from Action Plan/Tracking doc)		

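### The detailed procedure for falls and adverse events to week 6 describes no contact with people who miss class, and the protocol's sections disagree on whether telephone calls cover that period

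*Combined protocol and SAP*

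**What the plan says.** The protocol has a dedicated section for adverse-event recording from baseline through week 6. Participants note falls and symptoms daily on a form (Action Plan or Activity Tracker), and "At each session, the instructor will collect the forms, make copies for study documentation, and return them to the participants". Events may also be reported "or verbally, in-person or by telephone, the instructor will provide appropriate clinical assessment", and events that occur during a class are handled there. Data Collection during the Program confirms that the copied sheets are the record of falls and adverse events. The table in 6 Week Data Collection Assessment draws its falls and adverse-event rows from the same documents.

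Under Feasibility Data, the class instructor tracks cancellations and no-shows. No enquiry about safety is attached to them.

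Telephone contact is described in two places. The safety paragraph beside Figure 2, under Intervention Program, says of falls, injuries and adverse events that "the research assistant will conduct calls bi-weekly telephone calls to collect these data", with no start or end date. The section for week 6 to 6 months begins "To identify adverse events after the regular class sessions have been completed, participants will record the events in their tracking forms". It gives the calls to a blinded assessor, separate from the outcomes assessor and from the management and intervention teams, who "will contact the participants every 2 weeks by telephone to inquire about any events that have occurred" using a standard script.

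The Statistical Analysis Plan summarises falls and adverse events as n and %. It gives no rule for participants whose follow-up for events is incomplete.

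**The concern.** Safety is part of Aim 3, and the first six weeks are the main period of supervised group exercise (the booster at week 12 is the other). The protocol itself expects fatigue, soreness, falls and injuries from exercise. Any of these is a plausible reason to stop coming, so absence may be related to the very events being counted.

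Once classes are over, the plan provides active calls, presumably because there is no longer a class at which to collect forms. Someone who stops attending in week 3 is already in that position, yet the detailed procedure gives that person no call until after week 6.

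Two things are at stake. The first is completeness: the arm that loses more people after a fall or injury would look safer than it is. The second is timing: same-day notice of an unanticipated problem to the principal investigator can start only when staff learn of the event. The study is also meant to inform a formal trial, so if its in-trial fall counts feed into that planning, an undercount would carry over.

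**Working it through.** The plan states no figure on this point, so there is none to reproduce. The check sets the collection routes side by side and then gives an illustration under stated assumptions.

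**Step 1. Which routes reach a person who stops attending before week 6?**

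| Route | Where described | Reaches a non-attender in weeks 0–6? |
|---|---|---|
| Form collected at class | Baseline-to-week-6 section | No |
| Event during class | Same section | No |
| Report by the participant, including by telephone | Same section | Only if the participant starts it |
| No-show log | Feasibility Data | Staff know of the absence, but no contact is described |
| Bi-weekly call by the research assistant | Safety paragraph, Intervention Program | Unclear: no time window |
| Two-weekly scripted call by the blinded assessor | Week-6-to-6-months section | No: placed after classes end |
| Form at the week-6 assessment | 6 Week Data Collection | Later, if the person comes and has kept the form |
| Falls questions at 3 and 6 months | 3 Month and 6 Month Data Collection | Later, by recall; recall window not given in the text |

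Whether any staff-initiated contact exists in weeks 0–6 therefore depends on one undated sentence. That sentence differs from the detailed section on who calls and on when calls are made.

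**Step 2. How many falls could be missed?** The documents give no attendance figures, so these inputs are assumptions:

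- a, the share of an arm that stops attending: 10%, 20% or 30%;
- k, their fall rate relative to attenders: 1, 2 or 3;
- stopping halfway through the six weeks on average, so half of their time is unobserved;
- every fall before stopping is recorded and none after stopping is ever recovered.

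With the attenders' rate set to 1, total falls are proportional to (1 − a) + a·k, and falls after stopping to 0.5·a·k. So:

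missed share = 0.5·a·k / [(1 − a) + a·k]

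| a | k = 1 | k = 2 | k = 3 |
|---|---|---|---|
| 10% | 0.05/1.0 = 5% | 0.10/1.1 = 9% | 0.15/1.2 = 12.5% |
| 20% | 0.10/1.0 = 10% | 0.20/1.2 = 17% | 0.30/1.4 = 21% |
| 30% | 0.15/1.0 = 15% | 0.30/1.3 = 23% | 0.45/1.6 = 28% |

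**Step 3. Sensitivity to timing.** If these people never attend at all, the factor 0.5 becomes 1 and each share doubles, giving 10% (a = 10%, k = 1) to 0.9/1.6 = 56% (a = 30%, k = 3).

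**Step 4. In counts.** The Introduction cites 16% of older adults reporting a fall in 3 months. At a constant hazard, with 13 weeks in 3 months, the six-week risk is 1 − (1 − 0.16)^(6/13) = 7.7%. With 24 per arm (48 split equally; the ratio is not stated), that is 24 × 0.077 ≈ 1.9 fallers. Treating fallers and falls alike, 5–28% of 1.9 is about 0.1 to 0.5 per arm. The trial enrols people at increased risk, so its rate may be higher. The missed share does not depend on that rate.

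**The case against.** A reader might infer that events to week 6 come only from attenders and self-reporters, that a non-attender has no active route at all, and that such people leave the safety count. The documents do not support this. The safety paragraph promises bi-weekly calls and does not confine them to the period after classes. Missing class is not withdrawal: a participant can telephone, bring the form to the week-6 visit, mention an earlier event in a later call (which asks about any events), or answer the falls questions at 3 and 6 months. Control participants also continue one-on-one physical therapy. The appendices with the call script and the 6-week form are not in the text and may contain a direct question.

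All of that stands against the stronger reading, but it does not remove the gap. The later routes are delayed, depend on recall or on the same form, and need the person to stay in contact. The text describes no path from a control participant's ordinary therapy visits to the study's adverse-event log. The undated sentence about calls conflicts with the detailed section, and staff who followed the detailed section would make no calls before week 6.

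A second objection is that the percentages rest wholly on assumed inputs and allow for no recovery. That is right: they are a ceiling on what later recovery could leave missing, given halfway stopping, and not an estimate. The model also fits the suspected mechanism only roughly. A fall that causes someone to stop may come after the last form handed in and be missed, or may happen in class and be recorded.

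A third is that the absolute effect is small, probably less than one faller per arm, in a study that is not powered to compare groups. This limits the consequence. But when only a few events are expected, each one missed changes the safety description noticeably.

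**Conclusion.** The concern holds in this form. The detailed procedure to week 6 relies on attendance or self-report and describes no contact with people who miss class, and the protocol is inconsistent on whether, and by whom, calls are made in that period. If the two detailed adverse-event sections are followed as written, falls and adverse events in people who stop attending are likely to be under-recorded or learned of late. The week-6 visit, the later calls and the 3- and 6-month questions reduce this without closing it.

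The size is unknown. Under halfway stopping by 10–30% of an arm and a fall rate 1–3 times that of attenders, 5–28% of that arm's falls would be missed if none were recovered later. If the undated calls in fact run from baseline in both arms, the gap largely disappears and what remains is an inconsistency to correct.

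**What to change.** Reconcile the safety paragraph under Intervention Program with the two adverse-event recording sections. State that the existing scripted call, every two weeks and by the same blinded caller, starts at baseline and covers weeks 0–6 for all randomised participants in both arms, on one schedule, whatever their attendance. Use these calls alongside the forms for the 6-week falls and adverse events, and flag the source of each event. In the Statistical Analysis Plan, add a report by arm of the number of participants without complete safety contact.

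A fixed schedule is preferable to a call triggered by a missed session. The arms have 8 and 6 sessions, so absence-based triggers would arise unequally, and calls tied to arm-specific class dates could reveal the assignment to the blinded caller.

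Cost: 6 weeks ÷ 2 = 3 short calls per participant, or 3 × 48 = 144 in all, already implied by the safety paragraph. Where the baseline visit falls a full two weeks before the first class, a fourth call may be needed. The script, the form and the caller's role exist. The downside is a mixed diary and telephone source for events, which the source flag makes visible.

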The proposed project, Living In Fitness Together (LIFT) tests the feasibility and preliminary efficacy of a group-based PT fall prevention program using a within-group peer coaching intervention to improve outcomes for older adults at risk for falls by promoting sustained patient engagement in exercise and physical activity. The program will consist of group-based physical therapy for balance, strength, flexibility, and mobility training combined with a behavioral theory-based goal-achievement and peer-coaching training intervention targeting self-efficacy for the patients/group participants. It consists of 8 group sessions over 6 weeks plus one group booster session delivered by a physical therapist (PT) and trained staff. The program is designed to: 1) deliver progressive, tailored, and challenging exercise intervention for older adults at risk for falls; 2) empower older adults to achieve the required milestones for exercise and physical activity through training in theory-based behavior change, self-management, peer support and peer-coaching applied among the group participants; 3) incorporate evidence-based home safety intervention with necessary support for implementation of modification recommendations. By focusing on peers empowering each other within PT intervention as the center of exercise-based fall prevention for long-term patient engagement, this project will provide an innovative model for successful fall prevention.

Our Specific Aims are to:

1. Assess the feasibility of implementing the peer-coaching program in the physical therapy practice context by measuring enrollment, attendance, and completion of the program.
2. Evaluate whether the LIFT Fall Prevention program creates long-term behavior change as measured by exercise adherence at 6 months.
3. Evaluate safety and preliminary efficacy of the LIFT Fall Prevention program among 48 patients within an outpatient physical therapy practice. Safety will be assessed using self-reported falls, injuries, and adverse events. To support trial design for a future comparative

trial, we will measure indicators of initial efficacy including lower extremity strength and function, balance, balance confidence, concern about falls, mobility, physical activity, self-efficacy for exercise, and exercise adherence.

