## Intervention Program

### Exercise Component

The design of the group exercise intervention is based on the evolving evidence for exercise and fall prevention. This component was modified based on the evidence-based Otago Exercise Program (OEP), and leverages preliminary research in a group-based modification. It was designed to meet PT best practice recommendations for fall prevention from the APTA Clinical Guidance Statement results of Sherrington et al.'s updated exercise meta-analysis and best practice recommendations, and Power and Clifford's review: *Characteristics of optimum falls prevention exercise programs for community-dwelling older adults*. This includes progressive, challenging exercise for strength, balance training, mobility and gait training. The intervention will also meet physical activity recommendations from the American College of Sports Medicine (ACSM) and American Heart Association (AHA).

The strengthening /resistive and balance/neuromotor exercise components are based on the Otago exercise program with the addition of UE strengthening as recommended by ACSM guidelines. Cardiorespiratory/endurance exercise will be encouraged through an individualized progressive walking home program with the use of accelerator meter for feedback once cleared by the physical therapist. Flexibility exercises will be incorporated into the exercise program or within the peer coaching session.

The program frequency is two sessions/week for two weeks, decreasing to one time/week for 4 weeks. An additional group booster session will be scheduled 3 months post initiation of the program. The hour sessions will be divided between PT and a trained provider, initially forty five minute sessions for the first two weeks, for the physical components and education for tracking home exercise program. The exercise component will decrease to thirty minutes and increased time will be allotted to the goal-achievement component of the program.

Intensity for all components will be measured by self-report using the modified Borg Rating of Perceived Exertion (RPE) scale from "somewhat hard" (5-6) to "vigorous" (7-8). Exercise duration will be adjusted according to intensity.

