## Control Program

The control group will continue with "usual care" one-on-one physical therapy. In addition, they will attend a control group class that provides social interaction and interesting health information. They will be asked to track when and how much they do their PT home exercise program, walking, and any falls or adverse events or problems. Below is a description of the control group class.

**"Healthy YOUiversity"** is a program developed by Boston University and Mt Ascutney Hospital and Health Center (MAHHC) for the Living In Fitness Together Research Study to provide group education about activities and behaviors that promote healthy living. This 6-session program includes the following topics:

**Home Safety:** Content will be provided in the participant binder to address the range of ways to enhance safety inside and outside of the home. This content will be reviewed in the orientation session so that questions can be answered and participants can expect the OT's call. A Home Safety Assessment by an Occupational therapist will be offered, as described above in the Home Safety Assessment section.

**Session 1. New Stress Paradigm.** This session will discuss stress within the context of the Energy In - Energy Out paradigm. Participants will learn examples of healthy activities and choices across a range of topics including nutrition, sleep, positive thinking, social support, meaningful activities, and exercise. Activities and choices that may deplete energy and overall health will be discussed. Tools such as visual imagery, mindfulness, breathing exercises, and simple techniques to enhance healthy sleeping patterns will be presented. Handouts will be provided in the participant binder.

**Session 2. Nutrition.** This session will teach the heart healthy diet as outlined by The American Heart Association, National Institutes of Health and the American Medical Association. Handouts from government websites will be provided in the participant binder.

**Session 3. Leisure Education for Quality of Life.** This session will explore the PLESS approach to including a variety of healthy leisure activities.

- **P:** Physical
- **I:** Intellectual
- **E:** Emotional/Relaxing
- **S:** Social
- **S:** Spiritual/Meaningful.

**Session 4. Social Capital** This session will define social capital and how it aids a healthy lifestyle. Examples will be discussed including sharing information and resources, providing assistance, and building trust.

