**6 Month Data Collection (See Appendix U)**

Both Groups		Intervention Only
Performance-based Measures	Self-report Measures	
4-stage balance	LLFDI community mobility short form or CAT	
TUG	FES-I	
30-second Chair Stand	ABC-6	
DGI	Barriers Self-Efficacy	
	Get up from floor	
	Steps/Day	
	Exercise Adherence Walking, Strength, Balance	LIFT program overall questions
	Falls questions	Peer-Coaching Questions (full)

A summary of the program content is provided below.

	Exercise	Goal-Achievement
Week 1		
Class 1	Time: 45 min	15 min
	Content: Learn warm up, strength, balance and flexibility ex's, overall ex goals (2-3X/week: 2-3 sets 70% 1 RM; balance challenge, walking 3x/week), estimating 70% 1RM; safety, logging activity, symptoms, falls	Group building/Ice-breaker activities Homework: Look at the Action Plan
Class 2	45 min	15 min
	Learn warm up, strength, balance and flexibility ex's, overall ex goals (3X/week: 1 set of 10 70% 1 RM; balance challenge, walking 3x/week), estimating 70% 1RM; safety, logging activity, symptoms, falls	Work on Action Plan Introduction to Self-awareness
Week 2		
Class 3	45 min	
	How to progress activity (PT to determine by self-report of PEI and if able to perform 2 sets of resisted exercises progression of weight. Determine safety of decreasing support with balance and standing exercises.	15 minutes
		Problem-solving skills
		Self-awareness
Class 4	45 min Warm up, strengthening exercises, flexibility, balance exercises with progression of decreasing support	15 minutes
	Ramp/stairs	Self-Assessment
	Introduce methods of transferring safely to floor and up with modifications	
Week 3		
Class 5	30 min Warm up, strengthening exercises, flexibility, balance exercises with progression of decreasing support.	15 min Problem-solving
		15 minutes peer coaching
		Video; fall-specific coaching; roles and responsibilities
Week 4		
Class 6	30 min Encourage participants co-lead exercises. Warm up, strengthening exercises, flexibility, balance exercises with progression of decreasing support	30 min
	Set up obstacle course with foam, rocker board, static balance challenges, steps, reaching with and without UE support	Peer-coaching skills (active listening)
		Break-out in pairs
		Report back
Week 5		

	Exercise	Goal-Achievement

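### To week 6, falls and adverse events are logged only through each arm's own unblinded instructor, with no allocation-blind source, and the plan contradicts itself on who makes the two-weekly calls

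*Combined protocol and SAP*

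**What the plan says.** **Weeks 0 to 6.** Under Adverse Event Recording from the Baseline Data Collection through Week 6, participants record falls and other events daily. Then: "At each session, the instructor will collect the forms, make copies for study documentation, and return them to the participants". The instructor also fills out the Adverse Event Form when a participant reports an event or has one in class. The LIFT arm uses the Action Plan and the control arm the Activity Tracker. Feasibility Data names a separate class instructor for each arm.

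**Sessions.** For LIFT, the Introduction says "It consists of 8 group sessions over 6 weeks plus one group booster session", and Exercise Component says "The program frequency is two sessions/week for two weeks, decreasing to one time/week for 4 weeks". For the control class, Control Program says "This 6-session program includes the following topics". The control topics are health education, and controls continue usual-care physical therapy.

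**After week 6.** Under Adverse Event Recording from Week 6 through Study Completion, "a blinded assessor (separate from the outcomes assessor, study management and intervention teams) will contact the participants every 2 weeks by telephone", following a standard script intended to keep information consistent and preserve blinding. This assessor passes completed forms to the research assistant.

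**The other account of the calls.** The safety-monitoring paragraph after Figure 2 says "the research assistant will conduct calls bi-weekly telephone calls to collect these data". It gives no start week and does not mention blinding.

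**Visit tables.** At 6 weeks the listed fall source is "Falls (from Action Plan/Tracking doc)". The 3-month table lists the diary and falls questions. The 6-month table lists "Falls questions".

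**Analysis.** The Statistical Analysis Plan summarises safety as n and %, and says the study is not powered for differences between groups.

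**The concern.** Safety is part of Aim 3, and the first six weeks hold all the regular supervised group exercise. The plan recognises that who asks about events, and how, affects what is recorded: it prescribes a separate blinded caller and a script. That protection covers only the period after the classes end.

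Before then, whether an event reaches the master log depends on an instructor who knows the assignment. Closer observation in LIFT could produce an apparent excess of events; an instructor's expectations could hide a real one. At stake are the reading of falls and adverse events by arm, and the investigator's conclusion at continuing review about the pattern of events. Any fall rates from this period carried into the next trial's sample-size calculation would also be affected.

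The conflict over the caller is a separate matter. If the research assistant who keeps the master log makes the calls, the blinding described for weeks 6 to 26 may not exist.

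**Working it through.** **1. Session counts.** LIFT: 2 per week × 2 weeks + 1 per week × 4 weeks = 8, which reproduces the stated figure and matches Classes 1 to 8 in the program summary. Control: Sessions 1 to 6 are listed, so 6. The ratio is 8/6 = 1.33.

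**2. What 8 versus 6 could do to capture.** Let q be the assumed chance that one form collection logs an earlier event not yet logged. An event with k sessions still to come is logged with probability 1 − (1 − q)^k. Assume events spread evenly over weeks 0 to 6, weekly control sessions (the plan does not give their spacing), and the same class weekday in both arms. Write S(a..b) for the sum of 1 − (1 − q)^k over k = a to b.

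*Classes at the end of each interval* (LIFT at weeks 0.5, 1, 1.5, 2, 3, 4, 5, 6; control at 1 to 6):
- LIFT = [½·S(5..8) + S(1..4)]/6; control = S(1..6)/6.
- q = 0.1: LIFT (½ × 1.9693 + 0.9049)/6 = 0.315; control 1.7830/6 = 0.297; ratio 1.06.
- q = 0.3: LIFT (½ × 3.5743 + 2.2269)/6 = 0.669; control 3.9412/6 = 0.657; ratio 1.02.

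*Classes at the start of each interval* (LIFT at weeks 0, 0.5, 1, 1.5, 2, 3, 4, 5; control at 0 to 5):
- LIFT = [½·S(4..7) + S(0..3)]/6; control = S(0..5)/6.
- q = 0.1: LIFT (½ × 1.7437 + 0.5610)/6 = 0.239; control 1.3144/6 = 0.219; ratio 1.09.
- q = 0.3: LIFT (½ × 3.3918 + 1.4670)/6 = 0.527; control 3.0588/6 = 0.510; ratio 1.03.

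The range is therefore about 1.02 to 1.09, falling to 1.00 as q approaches 1. The effect is small because LIFT's two extra sessions fall in weeks 1 and 2; from week 3 both arms are taken to meet weekly.

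**3. Routes side by side, weeks 0 to 6.**

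| | LIFT | Control |
|---|---|---|
| Diary | Action Plan | Activity Tracker |
| Who collects it and completes the form | LIFT instructor | Control instructor |
| Supervised exercise seen by that person | Yes | No; class is education |
| Where supervised exercise takes place | In class | Usual-care physical therapy |
| Event-form role for the treating therapist | Yes | None stated |
| Scripted blinded call | Not before week 6 | Not before week 6 |
| Falls at the 6-week visit | From diary | From diary |

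The training section for outpatient therapists covers the study and eligibility only. A control event during physical therapy thus reaches the study only if the participant writes it down or reports it. Therapeutic Recreation Services adds that, for controls, the recreation therapist tracks attendance with no further documentation. That may refer to chart notes only, but it sits awkwardly beside the event-form duty.

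**4. The two accounts of the calls.** After Figure 2 the caller is the research assistant. In the week 6 onward section it is a blinded assessor, separate from study management, who hands forms to the research assistant. These are two people, so both statements cannot be followed. The first has no start week; the second starts at week 6.

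**The case against.** The strongest case against has five parts.

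- *The record is the participant's own daily diary in both arms.* This stands against the session count. Copying a diary more often adds no diary days. A reader might infer that a third more sessions means a third more recorded events; that needs logging proportional to contacts. Nor may every event be given all 8 or all 6 chances, since an event in week 5 meets only one or two sessions in either arm. The diary does not answer the point that an unblinded person decides what goes on the form.
- *The caller conflict cannot bias one arm against the other.* Correct. It applies to both arms alike and is a contradiction to reconcile, not a source of difference between them.
- *The visit tables are not the whole surveillance system.* Also correct. A reader might infer from the 6-month table that late falls come from questions alone, but tracking forms and two-weekly calls run to 6 months. The fall items are common to both groups.
- *No formal safety test is planned.* This stands, and limits the consequence to how descriptive counts are read.
- *Instructors cannot be blinded and must handle in-class events; controls have other clinical contact and can report verbally or by telephone.* True, and the fix leaves this in place. The other contact in usual-care therapy carries no stated duty to report to the study.

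Two uncertainties remain. The calls described after Figure 2 may already be meant to cover weeks 0 to 6, though without stated blinding. The 6-week form (Appendix S) was not available; only its summary table was.

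**Conclusion.** The concern holds in a limited form. As written, event counts by arm for weeks 0 to 6 rest on unblinded, arm-specific capture that differs in kind, with no allocation-blind source beside it. The direction of any distortion is unknown, and the documents give no figure from which to size it. The session count alone probably contributes little: a ratio of about 1.02 to 1.09 for q from 0.3 to 0.1, given evenly spread events, weekly control sessions and matching class days. That the instructors are unblinded is an inference, but a safe one, because each delivers one arm's class.

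The documents do not support saying that the safety results are invalid, or that a true effect of exercise could never be told apart from reporting. Safety is descriptive, and separating in-class events would remove part of the ambiguity. The point is worth acting on because the change is cheap. The contradiction about the caller should be reconciled in any case.

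**What to change.** 1. **Reconcile the calls.** In the safety-monitoring paragraph after Figure 2, replace the research assistant with the separate blinded assessor named in the week 6 onward section. State the call period there, for both arms.
2. **Add a blinded fall source at 6 weeks.** Put the falls questions already used at 3 and 6 months on the 6-week form for both arms, with recall back to baseline. Have the blinded data collector ask them, after a short reminder not to reveal group. State explicitly that this collector is blinded at 6 weeks; the detailed procedure is written only for baseline.
3. **Tabulate by setting.** In the safety summaries, show in-class events separately from events outside class, by arm.

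Keep instructor reporting of events and same-day notification unchanged.

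**Cost.** Protocol wording, one extra table split, and a few questions at a visit already held, with a small risk of unblinding the data collector. Item 2 covers falls only; other adverse events to week 6 would still come through the instructors.

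**Optional.** Starting the scripted blinded calls at baseline would cover those too. That is 6/2 = 3 calls per person, or 48 × 3 = 144, against about 48 × 10 = 480 already planned for weeks 6 to 26. It costs nothing extra if the paragraph after Figure 2 already intends those calls. Calls made while classes are running carry a greater risk of unblinding the caller.
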